9.1. Statistical and Analytical Plans (SAP)

Baseline demographics including age, weight, current medications, and general medical condition will be collected anonymously.

For each of the subjects, 10 intra-arterial blood pressure measurements will be collected and 10 wristband measurements will be collected at the same time points.

Systolic blood pressure measurements will be compared using an acceptable standard deviation of 10 mm Hg (\pm 5 mm Hg).

Diastolic blood pressure measurements will be compared using an acceptable standard deviation of 10 mm Hg (\pm 5 mm Hg).

Mean arterial pressure measurements will be compared using an acceptable standard deviation of 5 mm Hg (+/- 2.5 mm Hg).

The percentage of blood pressure measurements falling within the acceptable standard deviation will be compared.

The percentage of blood pressure measurements for each patient falling within the acceptable standard deviation will also be compared.

9.2. Statistical Hypothesis

The hypothesis is that >90% of wristband blood pressure measurements will be within the accepted standard deviation when compared to the intra-arterial blood pressure measurements.

9.2.1. General Approach

All statistical analysis for this study will be performed by [name], MD, MPH using Stat 15 software when needed.

9.2.2. Analysis of the Primary Efficacy Endpoint(s)

N/A

9.2.3. Baseline Descriptive Statistics

N/A

9.2.4. Planned Interim Analysis

N/A

9.3.1. Determining the reference BP

The invasive SYS and DIA BP values shall be determined from the recordings. (The BP reading will be recorded beat to beat, without any averaging, from the A-line and from the LiveMetric device). The mean and experimental standard deviation of the SYS and DIA BP from the recordings will be determined.

Since there is no cuff inflation interruption by the LiveMetric device, the A-line ranges shall be determined from the recording for a duration of 30 seconds, while simultaneously recording the same period of the data point from the LiveMetric device.

The reference SYS is defined as the range of a ± 1 experimental standard deviation around the mean value of the invasive systolic BP values obtained during the data point range performed by the LiveMetric device. The reference DIA BP is defined as the range of ± 1 experimental standard deviation around the mean value of the invasive diastolic BP values obtained during the same period.

Isolated VPB's shall be addressed by removing the pressure pulse associated with the VPB and the following compensatory beat.

If the value obtained from the LiveMetric determination lies within the range of the reference BP as determined in (**Error! Reference source not found.**), assign an error of 0 mmHg (0 kPa) to this determination.

If the value obtained from the LiveMetric determination lies outside the range of the reference BP as determined in (**Error! Reference source not found.**) subtract the value of the determination from the adjacent limit of the range of the variation of BP. That difference represents the error for this determination.

The arithmetic mean of the error is calculated and its experimental standard deviation from the errors of each recording for each BP value (SYS & DIA) and determination for each patient.

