7.7. Safety Oversight

It is the responsibility of the Principal Investigator to oversee the safety of the study at his/her site. This safety monitoring will include careful assessment and appropriate reporting of adverse events as noted above, as well as the construction and implementation of a site data and safety-monitoring plan. Medical monitoring will include a regular assessment of the number and type of serious adverse events.

8. Clinical Monitoring

PI will be conducting monitoring to ensure safety of subjects.

9. Statistical Considerations

Data from the A-line monitor and from the LiveMetric device shall be collected and processed using a validated Software. Categorical parameters shall be presented in percentages and will be compared using X² testing. Continuous variables shall be reported as mean \pm standard deviation and will be compared using the Student's t-test. Correlation shall be determined via linear regression analysis. Agreement shall be determined via the Bland and Altman technique. The analysis shall be conducted for intermittent values by applying the reference ISO 81060-2:2013.

The LiveMetric device shall provide values for each intermittent session and shall be compared to a range measured by the A-Line (data point). The data point is defined as the interval between the lower and higher value read by the A-Line, providing: the interval is no less than 30 seconds; the difference range from the reference device is less than the permissible highest range of 20 mmHg for SYS and 12 mmHg for DIA. Should the LiveMetric device read within the same range as the A-line, then the reading is considered accurate. However, if the reading is not within the defined range, then the error rate is defined as the range in mmHg between the closest edges of the reference reading to the values obtained by the LiveMetric device

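### The plan does not say whether Bland-Altman and the >90% within ±5 mmHg hypothesis use raw differences or errors zeroed inside the A-line band, and the choice can decide the result

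*Combined protocol and SAP*

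**What the plan says.** **Error rule.** Section 9.3.1 makes the systolic reference a "range of a ± 1 experimental standard deviation around the mean value of the invasive systolic BP values" over a 30-second window, with a matching definition for diastolic. For an in-band wristband value the analyst is to "assign an error of 0 mmHg (0 kPa) to this determination". For an out-of-band value the analyst is to "subtract the value of the determination from the adjacent limit of the range of the variation of BP". Section 9.3.3 takes the mean and SD of these errors, and section 9.3.4 ties the primary endpoint to the ISO 81060-2:2013 criterion.

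**A second band.** The opening text of section 9 (Statistical Considerations) has a rule of the same kind with a different band: "The data point is defined as the interval between the lower and higher value read by the A-Line", subject to a "permissible highest range of 20 mmHg for SYS and 12 mmHg for DIA". It adds: "Should the LiveMetric device read within the same range as the A-line, then the reading is considered accurate".

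**Agreement analyses.** The paragraph just before that one asks for linear regression and states: "Agreement shall be determined via the Bland and Altman technique". Section 9.1 sets tolerances of ±5 mmHg for systolic and diastolic pressure and ±2.5 mmHg for mean arterial pressure (MAP), and asks for the percentage of readings within them. Section 9.2 states: "The hypothesis is that >90% of wristband blood pressure measurements will be within the accepted standard deviation".

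Nowhere do the documents say which difference enters the Bland-Altman analysis or the percentages.

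**The concern.** A banded error is not a paired difference. It discards all disagreement inside the band and subtracts the half-width from everything outside it. That is the plan's chosen method for the ISO mean and SD, and it is not disputed here. Bland-Altman limits and a ±5 mmHg tolerance mean something else to a reader: how far the wristband is from the A-line.

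Section 9 places Bland-Altman directly before a paragraph that compares the wristband with an A-line range and defines error only from the range edge. An analyst following that text literally could carry the banded error into every agreement analysis. The only quantitative hypothesis in the plan could then be met or missed by the same device according to an unstated choice, and that choice could be made after the data are seen.

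**Working it through.** **Is there a figure to reproduce?** No. The documents give no expected within-tolerance rate, no limits of agreement, no device SD and no typical A-line SD. The sample size of 15 is taken from the standard.

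**Inputs from the documents.** Tolerance ±5 mmHg for systolic and diastolic (9.1); target >90% (9.2); zero error inside the band and distance to the nearer edge outside it (9.3.1); range cap 20 mmHg systolic and 12 mmHg diastolic (9).

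**Assumptions.** The raw difference D (wristband minus A-line mean) is normal with mean 0 and SD s. The half-width h is constant. Neither s nor h is given, so a range is shown.

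**Formulas.**
- Banded error: E = sign(D) × max(|D| − h, 0).
- |E| ≤ 5 exactly when |D| ≤ 5 + h. So the raw share is 2Φ(5/s) − 1 and the banded share is 2Φ((5 + h)/s) − 1.
- Var(E) = 2[(s² + h²)(1 − Φ(h/s)) − h·s·φ(h/s)]. The limits of agreement are ±1.96 × SD.

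**Worked case, s = 5, h = 4.**
- Raw share: 2Φ(1.0) − 1 = 68.3%.
- Banded share: 2Φ(1.8) − 1 = 92.8%.
- Var(E) = 2[41 × 0.2119 − 20 × 0.2897] = 5.78, so SD(E) = 2.41.
- Limits: ±9.8 raw, ±4.7 banded.

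| s | h | Within ±5, raw | Within ±5, banded | Limits, raw | Limits, banded |
|---|---|---|---|---|---|
| 4 | 2 | 79% | 92% | ±7.8 | ±5.1 |
| 5 | 2 | 68% | 84% | ±9.8 | ±7.0 |
| 5 | 4 | 68% | 93% | ±9.8 | ±4.7 |
| 8 | 5 | 47% | 79% | ±15.7 | ±9.0 |

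**What it takes to reach 90%.** The largest s that gives 90% is (5 + h)/1.645. On raw differences this is 5/1.645 = 3.04 mmHg. On banded errors it is 7/1.645 = 4.26 (h = 2) or 9/1.645 = 5.47 (h = 4). At those two SDs the share truly within ±5 mmHg is 76% and 64%.

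**Which h is plausible?** Take the cap as the lowest-to-highest spread of beats and assume 30 to 40 roughly normal beats per window. The expected range is then 4.08 to 4.32 SDs. Under the ±1 SD band, h is at most about 20/4.32 to 20/4.08 = 4.6 to 4.9 mmHg for systolic and 12/4.32 to 12/4.08 = 2.8 to 2.9 mmHg for diastolic. So h = 4 is near the top for systolic and out of reach for diastolic; h = 2 is possible for both. Under section 9's lower-to-higher band, h is wider: below 10 mmHg systolic and below 6 mmHg diastolic.

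**Direction.** The within-tolerance share cannot fall under banding, whatever h is. With constant h the error SD cannot rise either.

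**The case against.** The strongest reply is that the plan never says the agreement analyses run on banded errors.
- Section 9.1 pairs 10 intra-arterial with 10 wristband readings at the same time points, and section 9.2 compares wristband readings with intra-arterial readings. Neither speaks of error.
- Bland-Altman by its nature takes paired differences.
- MAP has a tolerance but no band, so its percentage can only be raw, and the systolic and diastolic percentages stand beside it.

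All of this stands. It makes raw differences the more natural reading, but it does not settle the matter, because section 9 itself defines accuracy and error from the A-line range.

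Three stronger readings are tempting, and the documents do not support them.
- A reader might infer that the plan will overstate agreement. What is shown is an unspecified input in conflicting text. If raw differences are intended, no result changes.
- A reader might halve the 20 mmHg cap and treat h = 10 as typical, which at s = 8 would turn 47% into 94%. The range must be below 20 mmHg, so 10 is not reached even under the wider band, and it is not a realistic ±1 SD half-width. With h about 5 the banded share is about 79%, and the hypothesis fails either way.
- A reader might infer that the primary endpoint is compromised. It rests on the ISO criterion, for which banding is the stated method.

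It is also fair to say that the verdict flips only over a limited span of device SDs. At s = 5 and the diastolic h of 2.9, for example, the banded share is 88.6%, still short of 90%.

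**Conclusion.** The concern holds as a conflict and an omission: the plan does not fix the difference behind Bland-Altman and the systolic and diastolic within-tolerance percentages, and regression likewise has no stated single A-line value where the reference is a range. Under zero bias, normal differences and constant h, banded errors would add about 13 to 25 percentage points in the cases with s of 4 or 5 mmHg and about 32 points at s = 8, h = 5. They would narrow the limits of agreement by roughly 30% to 50%. In two of the four tabulated cases the 90% line is crossed on definition alone. The effect would be negligible only if raw differences already lay almost wholly within ±5 mmHg or the A-line hardly varied within a window. The two band definitions, lower-to-higher in section 9 and mean ±1 SD in section 9.3.1, differ and need reconciling in any case. The plan should be changed before analysis; the ISO criterion itself is not in question.

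**What to change.** 1. Limit the banded error to the ISO mean and SD in section 9.3.3.
2. State in sections 9 and 9.1 that Bland-Altman and the within-tolerance percentages for systolic, diastolic and MAP use the wristband value (adjusted for lateral difference) minus the A-line mean over the same 30 s, and that regression uses those same two values. The lateral-difference limits in section 4.1 cover systolic and diastolic only, so say whether any adjustment applies to MAP.
3. Compute limits of agreement by a method that accounts for up to 10 readings per subject.
4. Report the raw mean and SD of the differences beside the ISO figures.
5. Use one band definition in sections 9 and 9.3.1.

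The cost is a few sentences and one extra table. No new data are needed, since section 9.3.1 already records beat to beat and computes the A-line mean. The downside is that the reported percentage and limits may look less favourable than banded ones.

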9.3.3. Data Analysis

The data set will be collected for clinical investigation purposes and will be processed and analyzed according to the formulas provided in the ISO 81060-2: 2013.

The lateral difference will be calculated initially as the average difference between the readings or determination made on each limb according to Formula:

$$LD = \frac{1}{3} \times \left(\sum_{i=1}^3 P_i - \sum_{j=1}^3 P_j \right);$$

i is the index for the determination on the limb used for the sphygmomanometer-under-test determination;

j is the index for the reading on the limb used for the reference reading.

Only data within the inclusion criteria as defined in section (**Error! Reference source not found.**) will be processed for the purpose of clinical investigations.

The mean value of the errors for SYS and DIA BP, \bar{x}_n of the n individual paired determination of the LiveMetric device as determined above for all subjects, will be calculated according to Formula:

$$\bar{x}_n = \frac{1}{n} \times \sum_{j=1}^n X_1$$

and Formula:

$$S_n = \sqrt{\frac{1}{n-1} \times \sum_{j=1}^n (X_i - \bar{x}_n)^2}$$

Where;

X_1 is the error of the ith individual determination as determined in (**Error! Reference source not found.**);

n is the total number of determinations;

i is the index for the individual determination.

Mean or standard deviation outside the specified ranges above, mandate further algorithm modification until subsequent testing with new data sets done in accordance with this protocol meets the above criteria.

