4.1. Description of Study Design

1. A medical professional will measure simultaneous non-invasive auscultatory readings to determine the lateral difference for later adjustment of calculation accordingly. Calculation of lateral difference is provided in section (**Error! Reference source not found.**). All data from a subject shall be excluded if: i) the lateral difference of the reference systolic BP readings is more than 15 mmHg (2,00 kPa); or ii) the lateral difference of the reference diastolic BP readings is more than 10 mmHg (1,33 kPa).
2. If subject's reading is eligible, the medical professional or research personnel will place the LiveMetric wristband on the opposite limb than the one having the A-line, providing the location of the placement has intact skin.
3. During the measurement stage, BP values are simultaneously recorded from the reference invasive A-line and the LiveMetric device. In addition, other vital signs from the monitoring equipment can be collected as available (ECG, Respiratory rate, Pleth, and HR). The invasive BP values and other vital signs are captured from the Vital Signs Monitor (available in the patient's room) and the LiveMetric device. A measurement session of 30 minutes will be conducted for each subject. During the measurements, no information from the device will be provided to the investigator or study personnel. All the data will be processed and analyzed post-measurement according to the following considerations as required by the standard: only up to 10 consecutive measurements per subject will be analyzed; measurement will be made over 30 seconds of recording; consecutive meas-

urement will be considered as the next 30 seconds following at least a 60 second interval. Measurement (data points) is defined as recording or acquisition of signal from the monitor. The medical professional will take off the wristband at the end of this process.

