4. All measurements will be processed and analyzed retrospectively according to the requirements of the standard (ISO 81060-2) as detailed below in section (**Error! Reference source not found.**). A 30-minute session of measurements will be conducted for each subject. All the data will be processed and analyzed post measurement according to the following considerations as required by the standard; only up to 10 consecutive measurements per subject will be analyzed; measurement will be made over 30 seconds of recording; consecutive measurement will be considered as the next 30 seconds following at least a 60 second interval.
5. All data points recoded during the first phase will be sent for processing and calibrating the algorithm. All the data points recorded during the second stage will be post processed by algorithm and results will be analyzed by an unbiased third party (bio-statistician).
6. Demographics of the subject will be anonymous collected from the electronic medical record – height, weight, age, current medications, and general condition.
7. Blood pressure measurements from both the wristband and the intra-arterial blood pressure monitor will be compared.

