5.6. Total Number of Participants and Sites

Recruitment will end when approximately 20 participants are enrolled. It is expected that approximately 20 participants will be enrolled in order to produce 15 evaluable participants.

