5.7.2. Handling of Participant Withdrawals or Termination

A subject may withdraw from the study at any time. If a subject withdraws, his or her data will not be included in this analysis. An additional subject will be needed to allow for the goal sample size to be achieved.

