13.2. Protocol Deviations

Any deviation in protocol will be reviewed by the investigators to determine if data from the involved subjects can be included. If not, additional subjects will be required to obtain the goal sample size.

A protocol deviation is any noncompliance with the clinical trial protocol, GCP, or Manual of Procedures (MOP) requirements. The noncompliance may be either on the part of the participant, the investigator, or

the study site staff. As a result of deviations, corrective actions are to be developed by the site and implemented promptly.

These practices are consistent with ICH E6:

- 4.5 Compliance with Protocol, sections 4.5.1, 4.5.2, and 4.5.3
- 5.1 Quality Assurance and Quality Control, section 5.1.1
- 5.20 Noncompliance, sections 5.20.1, and 5.20.2.

Protocol deviations must be reported to the local IRB per their guidelines. The site PI/study staff is responsible for knowing and adhering to their IRB requirements. Further details about the handling of protocol deviations will be included in the MOP.

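### The plan does not separate calibration from test patients, states no algorithm freeze, and does not say that the first test is the study's result

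*Combined protocol and SAP*

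**What the plan says.** **Calibration and test (4.1 step 5).** "All data points recoded during the first phase will be sent for processing and calibrating the algorithm". Data from a second stage are then run through the algorithm, and the "results will be analyzed by an unbiased third party (bio-statistician"). Neither stage is given patients, a number, dates or a time window, and no other section of the text available for review defines them.

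**Structure of the study.** The Protocol Summary describes an open, single-arm pilot. Section 4.1 gives each subject one 30-minute session, with at most 10 measurements analysed, and processes everything afterwards. Section 5.6 ends recruitment at about 20: "It is expected that approximately 20 participants will be enrolled in order to produce 15 evaluable participants". Section 9.5 sets the goal at 15 patients, which is also the minimum it takes from the standard.

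**Extra patients.** Section 5.7.2 provides for withdrawals ("An additional subject will be needed to allow for the goal sample size to be achieved") and 13.2 for deviations that make data unusable ("additional subjects will be required to obtain the goal sample size"). Neither mentions calibration.

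**After a failed test (9.3.3).** A mean or standard deviation of the error outside the limits would "mandate further algorithm modification until subsequent testing with new data sets done in accordance with this protocol meets the above criteria". Section 9.3.4 ties the primary endpoint to the success criterion of the standard. It does not say which algorithm version, or which test, decides it.

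**Safeguards.** During the session "no information from the device will be provided to the investigator or study personnel". Section 9 calls for validated software for data collection and processing.

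**The concern.** Accuracy against the arterial line is the only objective, so the value of a pass depends on the test being independent of the tuning. Two gaps bear on that.

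First, if the algorithm is calibrated on a patient and then tested on the same patient, the result may not show the accuracy that a new wearer would get. All processing is retrospective, so only a recorded freeze can show that second-stage signals did not shape the algorithm.

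Second, the rule in 9.3.3 ends only on a pass. If a failed first test is not declared the result, a later passing version can take its place in the record. A device that is outside the limits then has more than one chance to be called accurate.

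**Working it through.** The plan gives no power calculation or error rate for this point, so there is no figure to reproduce. The check is whether the stated numbers force calibration and test apart, and whether a second test fits inside this study.

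**1. Can one session supply both phases?** Inputs from 4.1: 30-second recordings, at least 60 seconds between them, a 30-minute (1,800 s) session, at most 10 measurements analysed.
- Time for *k* measurements = 30*k* + 60(*k* − 1) seconds.
- *k* = 10: 300 + 540 = 840 s = 14 min.
- *k* = 20: 600 + 1,140 = 1,740 s = 29 min.
- *k* = 21: 630 + 1,200 = 1,830 s, which exceeds 1,800 s.

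The session holds 20 spaced measurements, twice the number analysed. The two phases could be two halves of one patient's session, and nothing in the text excludes that.

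**2. What if calibration patients come out of the 15 evaluable?** Inputs: goal 15 and minimum 15 (9.5), at most 10 readings per patient (4.1).
- Margin = 15 − 15 = 0 patients.
- 15 × 10 = 150 readings. This equals the 150 in 9.5 if that figure is a study total. The sentence there attaches it to each patient, so this is an assumption.
- One calibration patient removed: 14 patients and at most 14 × 10 = 140 readings.

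**3. Can the spare enrolees do the calibration?** About 20 enrolled − 15 evaluable = about 5. Five calibration and 15 test patients would just fit (5 + 15 = 20), leaving none for attrition. But 5.6 gives the 20 as the number needed to yield 15 evaluable, and no text assigns any of them to calibration.

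**4. Does a second test fit?** Two disjoint test sets at the minimum need 15 + 15 = 30 evaluable patients. Recruitment stops at about 20, so a second full test does not fit.

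**5. What does re-testing do to the chance of a pass?** Let *p* be the chance that a device outside the limits passes one test. Assume no real improvement and a second, independent data set.
- At least one pass in two tests: 1 − (1 − *p*)² = *p* + *p*(1 − *p*).
- The added term *p*(1 − *p*) is positive for every *p* strictly between 0 and 1.

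The direction is therefore certain under those assumptions. The size is not, because *p* cannot be fixed from the documents. Section 9.3.3 prints no numeric limits for the mean or standard deviation. The within-patient correlation is not given. Section 9.3.1 sets the error to zero inside a band of ±1 standard deviation around the arterial-line mean, so errors will not follow a simple normal distribution.

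**The case against.** **The re-test rule is not an endless loop inside this study.** A reader might infer unlimited repeat looks. The documents do not support that: recruitment stops at about 20, the Protocol Summary expects one month, 9.2.4 plans no interim analysis, and 12.2 requires IRB approval of amendments. Requiring new data also bars re-testing on the data that failed. And 9.3.4 makes missing the criterion the same as missing the primary endpoint. All of this stands, and a later exercise is the better reading. What remains is narrower: re-testing is to be done under this same protocol, and no sentence says that a failed first test closes the study as a failure and is reported.

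**Overlap of patients is not shown.** This also stands. The about 5 spare enrolees could be the calibration group. The text leaves membership open; it does not say that patients are shared.

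**Safeguards exist.** Device output is withheld from staff during measurement, and a third party analyses the second stage. Both help, but neither fixes which patients or which algorithm version are tested. Validated software is not the same as a frozen device algorithm.

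**Two other inferences should not be drawn.** Section 9.2.1 says "All statistical analysis for this study will be performed by" one person whose name is removed. That might look like a conflict with the third party in 4.1, but the two could be the same person, so no contradiction can be shown. A reader might also infer that the publication policy in 13.4 exempts this study from reporting as a small feasibility study. The documents call it a pilot and never make that equation.

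**Conclusion.** The point holds in this form. Phase membership is undefined, no algorithm freeze is stated, and the first test is not declared the reported result. The first two follow directly from the text. The third rests on an ambiguity, since re-testing is best read as a later exercise.

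The size that can be stated is structural. The session holds 20 measurements where 10 are analysed, so shared patients are possible. The margin over the minimum of 15 evaluable is zero, so calibration patients cannot come out of the 15 without missing it. A second full test would need 30 evaluable patients against a stop of about 20.

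No probability of a false pass is claimed. A reader might want one from a normal-error model, or might conclude that re-testing matters only for a device just outside the limits. Neither is supported, because the zero-error band in 9.3.1 changes the error distribution and the numeric limits are not printed. The documents do not say that shared patients or unreported failures will occur. They leave room for both, which is enough to make a pass hard to interpret, and the gap should be fixed.

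**What to change.** **4.1 step 5:**
- Define the first phase and the second stage by patients and recordings.
- State that the 15 test patients in 9.5 contribute no calibration data. Either calibrate on earlier data, or give the number of calibration patients in 5.6 and do not count them toward the 15.
- Freeze and record the algorithm version before any second-stage wristband signal is processed.

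**9.3.3:** replace the open-ended re-test sentence with: *The first test of the frozen version is the result of this study and is reported, pass or fail. A modified version is tested as a new study whose report lists every earlier attempt.*

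**Cost.** If calibration uses earlier data, the change is wording only. If calibration patients are drawn from this study, each is additional to the 15 evaluable. They either use up the margin of about 5 that 5.6 keeps for attrition or require a higher recruitment stop. In both cases a failed first test must be reported.
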